4.7 Replacement of subjects

Patients enrolled in the safety run-in phase of the study may be replaced if they are not evaluable for DLT (i.e., patients did not receive study treatment or withdrawn from the study for reasons other than drug-related toxicity) will need to be replaced to provide adequate evaluation of safety at the tested dose level.

Patients enrolled in the safety run-in phase who withdraw from the study after completing the first treatment cycle (DLT period) will not need to be replaced on the study.

Patients enrolled in the expansion phase of the study will not be replaced.

5 ELIGIBILITY CRITERIA

This eligibility checklist is used to determine patient eligibility and filed with signature in the patient research chart.

Each patient must meet all of the inclusion criteria and none of the exclusion criteria for this study. Under no circumstances will there be exceptions to this rule.

Patient No. _____

Patient's Initials: (L,F,M) _____

5.1 Inclusion Criteria

Yes/No (Response of "no" = patient ineligible)

- _____ 5.1.1 Able to provide a written informed consent and any locally-required authorization (e.g., HIPAA in the USA) prior to performing any protocol-related procedures, including screening evaluations.
- _____ 5.1.2 Female age \geq 18 years at time of study.
- _____ 5.1.3 Eastern Cooperative Oncology Group (ECOG) performance status of 0 or 1.
- _____ 5.1.4 Postmenopausal, defined as meeting at least 1 of the following criteria:
 - Age \geq 60
 - Prior bilateral oophorectomy
 - Age $<$ 60 with a uterus AND amenorrhea for at least the past 12 months (in the absence of chemotherapy, tamoxifen, toremifene, or ovarian suppression)
 - Age $<$ 60 without a uterus AND follicular stimulating hormone (FSH) and estradiol in the postmenopausal range per local normal range
- _____ 5.1.5 Clinical T2-T4c, any N, M0 by AJCC 8th edition, with the goal being definitive surgery after completion of neoadjuvant therapy.
 - The tumor is palpable and its size can be measured bidimensionally by tape, ruler or caliper technique
 - The largest tumor diameter is $>$ 2.0 cm
- _____ 5.1.6 Pathologic confirmation of invasive breast cancer that is estrogen receptor (ER) positive with an Allred score of 6, 7 or 8. If an Allred Score is not reported on the diagnostic pathology report, ER positivity in $>$ 66% cells is eligible. If ER positivity is \leq 66%, the staining intensity (weak, intermediate, strong) is needed to calculate the Allred Score to determine eligibility.
- _____ 5.1.7 Invasive breast cancer is Human Epidermal Growth Factor Receptor 2 (HER2) negative defined as 0 or 1+ by immunohistochemistry (IHC) or with an in situ hybridization (ISH) ratio (HER2 gene copy/chromosome 17) $<$ 2.
- _____ 5.1.8 Documentation of mammogram and ultrasound [including ductal carcinoma in situ (DCIS) and invasive cancer] of the diseased breast performed within 60 days prior to enrollment. Mammogram for the unaffected contralateral breast is required within 12 months prior to enrollment.

_____ 5.1.9 Adequate organ and marrow function as defined below, laboratory values obtained \leq 14 days prior to enrollment:

- Hemoglobin \geq 9.0 g/dL
- Absolute neutrophil count (ANC) $\geq 1.5 \times 10^9/L$ (≥ 1500 per mm 3)
- Platelet count $\geq 100 \times 10^9/L$ ($\geq 100,000$ per mm 3)
- Serum bilirubin $\leq 1.5 \times$ institutional upper limit of normal (ULN). This will not apply to subjects with confirmed Gilbert's syndrome (persistent or recurrent hyperbilirubinemia that is predominantly unconjugated in the absence of hemolysis or hepatic pathology), who will be allowed only in consultation with their physician
- AST (SGOT)/ALT (SGPT) $\leq 2.5 \times$ institutional upper limit of normal.
- Serum creatinine clearance > 40 mL/min by the Cockcroft-Gault formula (1976) or by 24-hour urine collection for determination of creatinine clearance

_____ 5.1.10 Subjects must be willing to undergo a research biopsy at baseline and after one cycle of treatment and to provide tissue obtained at surgery for biomarker and correlative studies.

_____ 5.1.11 Subjects must be willing and able to comply with the protocol for the duration of the study including undergoing treatment and scheduled visits and examinations including follow up.

_____ 5.1.12 If taking herbal or natural remedies that may have immune modulatory effects, subjects must be willing to discontinue it prior to first dose of durvalumab.

_____ 5.1.13 Body weight > 30 kg.

5.2 Exclusion Criteria

Yes/No (Response of “yes” = patient ineligible)

_____ 5.2.1 Participation in another clinical study with an investigational product during the last 4 weeks.

_____ 5.2.2 Concurrent enrolment in another clinical study, unless it is an observational (non-interventional) clinical study or during the follow-up period of an interventional study

_____ 5.2.3 Inflammatory breast cancer defined as clinically significant erythema of the breast and/or documented dermal lymphatic invasion (not direct skin invasion by tumor or peau d'orange without erythema).

_____ 5.2.4 An excisional biopsy of this breast cancer.

- _____ 5.2.5 Hormone replacement therapy of any type, megestrol acetate, or raloxifene within one week prior to registration.
- _____ 5.2.6 Surgical axillary staging procedure prior to study entry. Note: Fine needle aspiration (FNA) or core needle biopsy of axillary node is permitted.
- _____ 5.2.7 Treatment for this cancer including surgery, radiation therapy, chemotherapy, biotherapy, hormonal therapy or investigational agent prior to study entry.
- _____ 5.2.8 Any previous treatment with a PD1 or PD-L1 inhibitor, including durvalumab
- _____ 5.2.9 History of another primary malignancy except for malignancy treated with curative intent and with no known active disease ≥ 5 years or adequately treated non-melanoma skin cancer or lentigo maligna without evidence of disease or adequately treated carcinoma in situ without evidence of disease e.g., cervical cancer in situ.
- _____ 5.2.10 History of ipsilateral invasive breast cancer regardless of treatment or ipsilateral ductal carcinoma in situ (DCIS) treated with radiotherapy or endocrine therapy or contralateral invasive breast cancer at any time.
- _____ 5.2.11 Current or prior use of immunosuppressive medication within 14 days before the first dose of durvalumab, with the exceptions of intranasal, inhaled, topical steroids, or local steroid injections (e.g., intra-articular injection); systemic corticosteroids at physiological doses, which are not to exceed 10 mg/day of prednisone, or an equivalent corticosteroid; or steroids as premedication for hypersensitivity reactions (e.g., CT scan premedication).
- _____ 5.2.12 Active or prior documented autoimmune or inflammatory disorders (including inflammatory bowel disease [e.g., colitis or Crohn's disease], diverticulitis [with the exception of diverticulosis], systemic lupus erythematosus, Sarcoidosis syndrome, or Wegener syndrome [granulomatosis with polyangiitis, Graves' disease, rheumatoid arthritis, hypophysitis, uveitis, etc]). The following are exceptions to this criterion:
 - Patients with vitiligo or alopecia
 - Patients with hypothyroidism (e.g., following Hashimoto syndrome) stable on hormone replacement
 - Any chronic skin condition that does not require systemic therapy
 - Patients without active disease in the last 5 years may be included but only after consultation with the study physician
 - Patients with celiac disease controlled by diet alone
- _____ 5.2.13 History of primary immunodeficiency.

- 5.2.14 History of allogeneic organ transplant.
- 5.2.15 Known allergy or history of hypersensitivity to durvalumab, or any excipient.
- 5.2.16 Uncontrolled intercurrent illness including, but not limited to, ongoing or active infection, symptomatic congestive heart failure, uncontrolled hypertension, unstable angina pectoris, cardiac arrhythmia, active peptic ulcer disease or gastritis, active bleeding diatheses, , or psychiatric illness/social situations that would limit compliance with study requirements or compromise the ability of the subject to give written informed consent.
- 5.2.17 Known active infection including **tuberculosis** (clinical evaluation that includes clinical history, physical examination and radiographic findings, and TB testing in line with local practice), **hepatitis B** (known positive HBV surface antigen (HBsAg) result), **hepatitis C**, or **human immunodeficiency virus** (positive HIV 1/2 antibodies). Patients with a past or resolved HBV infection (defined as the presence of hepatitis B core antibody [anti-HBc] and absence of HBsAg) are eligible. Patients positive for hepatitis C (HCV) antibody are eligible only if polymerase chain reaction is negative for HCV RNA. Note: This is applied only to patients with known infection. Screening tests for TB, hepatitis B and C, or HIV are not required.
- 5.2.18 Receipt of live attenuated vaccination within 30 days prior to receiving durvalumab. Note: Patients, if enrolled, should not receive live vaccine while receiving durvalumab and up to 30 days after the last dose of durvalumab.
- 5.2.19 Any condition that, in the opinion of the investigator, would interfere with evaluation of study treatment or interpretation of patient safety or study results.
- 5.2.20 Subjects with uncontrolled seizures.
- 5.2.21 Patients with multi-centric breast cancer (defined as more than one lesion is invasive breast cancer in the same breast separated by ≥ 2 cm of normal breast tissue
- 5.2.22 Major surgical procedure (as defined by the Investigator) within 28 days prior to the first dose of investigational product.

I certify that this patient meets all inclusion and exclusion criteria for enrollment onto this study.

Investigator Signature

Date

Time

6 TREATMENT PLAN

6.1 Administration Schedule

6.1.1 Aromatase inhibitors

Anastrozole will be administered at a fixed dose of 1 mg PO once daily (QD) regardless of the subject's weight.

On cycle 1 day 1 (C1D1), patients are to take anastrozole prior to the infusion of durvalumab. Patients will then be encouraged to take their daily dose of anastrozole at approximately the same time each day at their convenience. Doses must be taken at least 18 hours apart.

If patients need to switch to another AI for intolerance reasons (such as hot flash or joint ache) in the post DLT period, they will be given letrozole (2.5 mg PO QD) or exemestane (25 mg PO QD).

6.1.2 Durvalumab

Durvalumab will be administered as follows:

Durvalumab, 1500 mg via IV infusion Q4W (equivalent to 20 mg/kg Q4W) on Day 1 of each 28-day cycle for 6 cycles (6 doses – 6 months).

6.2 How Supplied, Stored, Packaged and Labeled

6.2.1 Commercial products

The aromatase inhibitors anastrozole, letrozole or exemestane are standard of care drugs and must be obtained from commercial sources. Please refer to the current FDA-approved package inserts provided with the medications or the Physicians' Desk Reference for instructions for preparation, handling, and storage.

6.2.2 Investigational drugs

The Investigational Products Supply section of AstraZeneca/MedImmune will supply durvalumab (MEDI4736) to the investigator as a 500-mg vial solution for infusion after dilution. Durvalumab will be supplied to the study as a commercial product.

6.2.2.1 Formulation/packaging/storage

Durvalumab (MEDI4736) will be supplied by AstraZeneca as a 500-mg vial solution for infusion after dilution. The solution contains 50 mg/mL durvalumab (MEDI4736), 26 mM histidine/histidine-hydrochloride, 275 mM trehalose dihydrate, and 0.02% weight/volume (w/v) polysorbate 80; it has a pH of 6.0. The nominal fill volume is 10.0 mL. Investigational product vials are stored at 2°C to 8°C (36°F to 46°F) and must not be frozen. Drug product should be kept in secondary packaging until use to prevent excessive light exposure.

6.3 Preparation and Administration

The dose of durvalumab (MEDI4736) for administration must be prepared by the Investigator or site designated investigational product (IP) manager using aseptic technique.

Fixed doses will be used based on an average body weight of 75 kg:

- Durvalumab: 1500 mg Q4W (equivalent to 20 mg/kg Q4W).

Total time from needle puncture of the vials to start of administration should not exceed 24 hours at 2 °C - 8 °C (36°F to 46°F) or 4 hours at room temperature.

Infusion solutions must be allowed to equilibrate to room temperature prior to beginning administration.

A dose of 1500mg (for patients >30kg in weight) will be administered using an IV bag containing 0.9% (w/v) saline or 5% (w/v) dextrose, with a final durvalumab (MEDI4736) concentration ranging from 1 to 15 mg/mL, and delivered through an IV administration set with a 0.2- or 0.22- μ m in-line filter. Add 30.0 mL of durvalumab (MEDI4736) (ie, 1500mg of durvalumab [MEDI4736]) to the IV bag. The IV bag size should be selected such that the final concentration is within 1 to 15 mg/mL. Mix the bag by gently inverting to ensure homogeneity of the dose in the bag.

Standard infusion time is 1 hour. In the event that there are interruptions during infusion, the total allowed infusion time should not exceed 8 hours at room temperature.

Do not co-administer other drugs through the same infusion line.

The IV line will be flushed with a volume of IV diluent equal to the priming volume of the infusion set used after the contents of the IV bag are fully administered, or complete the infusion according to institutional policy to ensure the full dose is administered and document if the line was not flushed.

If either preparation time or infusion time exceeds the time limits a new dose must be prepared from new vials. Durvalumab (MEDI4736) does not contain preservatives, and any unused portion must be discarded.

6.4 Monitoring of dose administration

Patients will be monitored before, during and after the infusion with assessment of vital signs at the times specified in the Schedule of Assessment. Patients are monitored (pulse rate, blood pressure) every 30 minutes during the infusion period (including times where infusion rate is slowed or temporarily stopped).

In the event of a \leq Grade 2 infusion-related reaction, the infusion rate of study drug may be decreased by 50% or interrupted until resolution of the event (up to 4 hours) and re-initiated at 50% of the initial rate until completion of the infusion. For patients with a \leq Grade 2 infusion-related reaction, subsequent infusions may be administered at 50% of the initial rate. Acetaminophen and/or an antihistamine (e.g., diphenhydramine) or equivalent medications per institutional standard may be administered at the discretion of the investigator. If the infusion-related reaction is Grade 3 or higher in severity, study drug will be discontinued. The standard infusion time is one hour, however if there are interruptions during infusion, the total allowed time from infusion start to completion of infusion should not exceed 4 hours at room temperature, with maximum total time at room temperature not exceeding 4 hours (otherwise requires new infusion preparation). For management of patients who experience an infusion reaction, please refer to the toxicity and management guidelines in **Error! Reference source not found.**appendix 1.

A 1 hour observation period is required after the first infusion of durvalumab. If no clinically significant infusion reactions are observed during or after the first two cycles, subsequent infusion observation periods can be at the Investigator's discretion (suggested 30 minutes after each durvalumab infusion).

Instructions for the management of infusion-related reactions or allergic reactions can be found in section 15.4.4 and Appendix 1.

6.5 Accountability and Compliance

The investigator will not supply investigational drug to any patient not enrolled in the study, or to any physicians or scientists except those designated as sub-investigators.

The investigator must ensure that patients receive study drug only from personnel who fully understand the procedures for dosing and administering the drug.

Each shipment of study drug for a study will contain an Investigational Drug Shipping Request (IDSR) form to assist the investigator in maintaining current and accurate inventory records.

The IDSR form will identify for each shipment the subject identification code (if applicable), the lot number, and the quantity of vials contained in the shipment. Upon receipt of the investigational drug, the designated recipient will visually inspect the shipment and verify the number and condition of vials received. The designated recipient will complete the lower portion of the IDSR form. A copy of the signed form is to be filed with the inventory/drug accountability records. The original completed form will be mailed back to Astra Zeneca in the envelope provided with the drug shipment.

Only authorized personnel should have access to the drug. For accurate accountability, the following information must be noted when drug supplies are used during the study: the patient identification, the lot number of the drug dispensed for that patient, and the date and quantity of drug dispensed. Study drug accountability records should also document receipt and return or destruction of study drug supplies.

Drug accountability records must be readily available for inspection by representatives of Astra Zeneca and are open to inspection by regulatory authorities at any time.

Compliance of the oral AI will be assessed and recorded by the investigator and/or study personnel at each patient visit. A dosing log will be used.

6.6 Disposition of unused investigational study drug

The site will account for all investigational study drug dispensed and also for appropriate destruction. Certificates of delivery and destruction must be signed.

Return of all drug supplies must be coordinated with Astra Zeneca prior to shipment. When unused drug supplies are returned, the number of vials being returned and the lot numbers should be noted in the site inventory log and the Investigational Drug Return Form provided by Astra Zeneca should be completed.

Upon completion of this study, appropriate site personnel should verify that all unused drug supplies have either been returned or destroyed and that no investigational drug remains in the investigator's possession. For all drug supplies that are not returned, officially signed and dated written documentation of proper disposal or destruction of the drug in accordance with the appropriate

institutional guidelines must be maintained in the drug accountability records. A copy of the drug accountability records must be returned to Astra Zeneca at the end of the study.

6.7 Concomitant Medications and Treatments

The Principal Investigator must be informed as soon as possible about any medication taken from the time of screening until the end of the clinical phase of the study (final study visit).

The following medications are considered exclusionary:

1. Any investigational anticancer therapy other than the protocol specified therapies
2. Any concurrent chemotherapy, radiotherapy (except palliative radiotherapy), immunotherapy, biologic or hormonal therapy for cancer treatment, other than any stated comparator or combination regimens. Concurrent use of hormones for non-cancer-related conditions (e.g., insulin for diabetes) is acceptable. Estrogen-containing hormone replacement therapy is not acceptable.
3. Herbal and natural remedies which may have immune-modulating effects.
4. Immunosuppressive medications including, but not limited to systemic corticosteroids at doses not exceeding 10 mg/day of prednisone or equivalent, methotrexate, azathioprine, and TNF- α blockers. Use of immunosuppressive medications for the management of investigational product-related AEs or in subjects with contrast allergies is acceptable. In addition, use of inhaled and intranasal corticosteroids is permitted. A temporary period of steroids will be allowed for different indications, at the discretion of the principal investigator (e.g., chronic obstructive pulmonary disease, radiation, nausea, etc).
5. Live attenuated vaccines within 30 days of durvalumab dosing (i.e., 30 days prior to the first dose, during treatment with durvalumab for 30 days post discontinuation of durvalumab. Inactivated vaccines, such as the injectable influenza vaccine, are permitted.

In addition, subjects should not donate blood while participating in this study or for at least 90 days following the last infusion of durvalumab.

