15.7 Protocol Deviations

A protocol deviation (or violation) is any departure from the defined procedures and treatment plans as outlined in the protocol version submitted and previously approved by the IRB. Protocol deviations have the potential to place participants at risk and can also undermine the scientific integrity of the study thus jeopardizing the justification for the research. Protocol deviations are unplanned and unintentional events.

Because some protocol deviations pose no conceivable threat to participant safety or scientific integrity, reporting is left to the discretion of the PI within the context of the guidelines below. The IRB requires the **prompt reporting** of protocol deviations which meet any of the following criteria:

- Exceptions to eligibility criteria.
- Intended to eliminate apparent immediate hazard to a research participant.
- Harmful (caused harm to participants or others, or place them at increased risk. harm - including physical, psychological, economic, or social harm).
- Possible serious or continued noncompliance.

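### Section 6.7 item 4 prohibits systemic corticosteroids up to 10 mg/day, the same dose range that exclusion criterion 5.2.11 accepts at entry

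*Combined protocol and SAP*

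**What the plan says.** Section 6.7 (Concomitant Medications and Treatments) gives a numbered list of prohibited medications. Item 4 begins "Immunosuppressive medications including, but not limited to systemic corticosteroids at doses not exceeding 10 mg/day of prednisone or equivalent" and goes on to name methotrexate, azathioprine and TNF-α blockers, with no dose attached to those three.

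Item 4 then makes exceptions:
- "Use of immunosuppressive medications for the management of investigational product-related AEs or in subjects with contrast allergies is acceptable"
- inhaled and intranasal corticosteroids
- "A temporary period of steroids will be allowed for different indications, at the discretion of the principal investigator"

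Item 2 of the same list adds that "Concurrent use of hormones for non-cancer-related conditions (e.g., insulin for diabetes) is acceptable".

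At entry, criterion 5.2.11 excludes immunosuppressive medication within 14 days before the first durvalumab dose. Among its exceptions are "systemic corticosteroids at physiological doses, which are not to exceed 10 mg/day of prednisone, or an equivalent corticosteroid".

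**The concern.** The two sections use the same drug class and the same 10 mg/day prednisone cut-off, but in opposite directions. Section 5.2.11 lets the low dose in, and 6.7 item 4 names that low dose as prohibited. A patient admitted under 5.2.11 who simply continues her steroid would be out of compliance as soon as treatment starts.

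At stake are consistent handling of concomitant medication and consistent deviation calls. A site that follows the literal text could log a deviation that means nothing, or stop a steroid that the eligibility criteria had accepted. The list is an operative one: section 7.2 limits supportive medication by reference to what is prohibited, and section 16.3.3 has monitors check adherence to the protocol.

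**Working it through.** No sample size, error rate or event count is involved, so the check is a comparison of text.

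**Step 1. The two rules side by side.**

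| Place | Period | Systemic steroid at 10 mg/day or less |
|---|---|---|
| 5.2.11 | 14 days before first durvalumab dose | Accepted, at physiological doses |
| 6.7 item 4 | Concomitant use on study | Named as prohibited |

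**Step 2. Do the different periods resolve it?** No. A stable daily dose runs through both. Section 6.7 itself reaches back to screening: "The Principal Investigator must be informed as soon as possible about any medication taken from the time of screening". No section tells a patient admitted under 5.2.11 to stop the steroid before treatment.

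**Step 3. Do the exceptions resolve it?** Only in part.
- Product-related adverse events, contrast allergy, and inhaled or intranasal use do not describe a stable systemic dose carried in from before entry.
- The temporary period at the principal investigator's discretion is not a general allowance for continuing use.
- Item 2 on hormones may cover steroid replacement.
- Criterion 5.2.12, which excludes "Active or prior documented autoimmune or inflammatory disorders (including inflammatory bowel disease" among other conditions, removes most patients who would take low-dose steroids for inflammatory disease.

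What is left is a patient on a stable low dose for a reason outside all of these.

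**Step 4. Which direction was meant?** A 10 mg/day prednisone level appears in six places:
1. 5.2.11
2. 6.7 item 4
3. the Appendix rule on permanent discontinuation (General Considerations)
4. Appendix, General Considerations, Grade 2
5. Appendix, Endocrinopathy, Grade 2
6. Appendix, Endocrinopathy, Grade 3 or 4

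Five of the six treat 10 mg/day or less as acceptable; only 6.7 item 4 does not. The four Appendix entries concern management of immune-related events, which 6.7 already exempts. They are evidence of intent and not a second conflict. Item 4 also reads oddly in itself: a dose ceiling belongs to a permission, and here it is attached to a prohibition.

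**Step 5. Are high doses let in?** Not clearly. Item 4 prohibits immunosuppressants generally and presents its examples as non-exhaustive, so doses above 10 mg/day are best read as still prohibited. The text is too broad rather than too permissive.

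**The case against.** The strongest reply accepts the mismatch and disputes its weight.

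- **The count of five in six flatters the case.** Three of the Appendix entries repeat one exception, limited to endocrinopathy patients who need continued steroid replacement. The fourth is a rule for stopping study drug when the steroid cannot be tapered. Elsewhere in the Appendix, resumption often waits for the taper to finish, which suggests low-dose steroid is not accepted generally during dosing. This stands. The point rests on 5.2.11 against 6.7 item 4, and the Appendix only supports the inference about intent.
- **An on-study rule may be stricter than an entry rule.** Criterion 5.1.12 does this for immune-modulating herbal remedies. But it says so, by requiring willingness to stop before the first dose. Steroids carry no such instruction, so the analogy does not remove the conflict.
- **Almost nobody is affected.** Hormone replacement may fall under item 2, 5.2.12 bars most inflammatory disease, and the investigator's allowance for temporary steroids has no defined limit. This largely stands, although none of these is an express allowance for continuing physiological doses.
- **The harm is contained.** For deviations that pose no conceivable threat, section 15.7 says "reporting is left to the discretion of the PI within the context of the guidelines below", and section 4.6.1 has no specific item stopping study drug for a listed concomitant medication. This also stands, with one reservation: 15.7 requires prompt reporting of possible continued noncompliance, and daily use of a listed drug could be argued to fall there.

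**Conclusion.** The inconsistency is real and the text of 6.7 item 4 is wrong as written. Confidence in the mismatch is high. That the intended wording was *exceeding* is an inference from 5.2.11, the Appendix and the structure of item 4, and needs the sponsor's confirmation.

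The size is small. The documents give no rate of chronic low-dose systemic steroid use, so no number of patients can be estimated, and it could be none. There is no effect on the mPEPI 0 endpoint, the analysis sets, or the rule based on 14 and then 42 evaluable patients. It is worth correcting because the prohibited-medication list is operative and the correction is nearly free.

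**What to change.** In 6.7 item 4, replace *not exceeding 10 mg/day* with *exceeding 10 mg/day*, after the sponsor confirms that this was the intent. Leave the existing exceptions in 6.7, criterion 5.2.11 and the Appendix unchanged.

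The cost is one phrase in the next amendment, with no change to sample size, visits or data collection.
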